### 9.2. Efficacy Analysis

#### 9.2.1. Analysis Sets

The statistical objective of the study is to characterize the loss of response with each randomized group after achieving response at Week 12 following open-label treatment with 200 mg PF-04965842 QD.

The primary analysis population for efficacy data will be the Full Analysis Set (FAS-RA) defined as all randomized subjects who are dispensed at least one dose of study medication. This is a responder-enriched population who are eligible to enter the randomized, double-blind period of the study. All analyses will be reported by treatment regimen/sequence. The primary efficacy endpoint and the key secondary efficacy endpoints will also be analyzed for the Per-Protocol Analysis Set (PPAS) defined as a subset of FAS-RA who had no major protocol violations. Major protocol violations would consist of not meeting [inclusion criteria](#) or meeting an [exclusion criteria](#) or not having taken the correct randomized treatment for at least 80% of the assigned amount or having taken a prohibited concomitant medication (as detailed in [Section 5.9.2](#)) or any other major protocol violation as determined by the clinical team or medical monitor prior to database lock. The subjects excluded from the PPAS will be determined and documented before the study is un-blinded. For all analyses, baseline value will be based on observations collected pre-dose.

An additional subgroup of subjects who have received at least one dose of rescue treatment (following a protocol-defined flare during the randomized, double-blind period) will also be defined as the FAS-RE subgroup. In addition to these subgroups, analyses will also be performed for all subjects participating in the open-label run-in period (defined as the FAS-OL subgroup).

### **9.2.2. Testing Procedure for Multiple Comparisons**

There are six key hypotheses to be tested for each pairwise comparison between two PF-04965842 doses (200 mg QD and 100 mg QD) and placebo, for the primary and key secondary endpoints. For these hypotheses, the familywise Type-I error rate will be strongly controlled at 5% using a sequential, gatekeeping procedure.

The procedure will first test the hypothesis of no difference for the primary endpoint between 200 mg QD and placebo at 5% level of significance. If this hypothesis is rejected, statistical significance will be assessed for the hypothesis of no difference for the key secondary endpoint between 200 mg QD and placebo at 5% level of significance. If rejected, the procedure will continue with the hypothesis of no difference for the primary endpoint between 100 mg QD and placebo and if rejected, continuing with the hypothesis of no difference between 100 mg QD and placebo for the key secondary endpoint. Finally, if all the above hypotheses are rejected, the procedure will continue with the hypothesis of no difference between 200 mg QD and 100 mg QD for the primary endpoint and if rejected, continuing with the hypothesis of no difference between 200 mg QD and 100 mg QD for the key secondary endpoint. All tests will be conducted at 5% level of significance. Statistical significance for subsequent tests will not be formally claimed if the previous hypothesis has not been rejected.

Hypotheses for all other endpoints not described here are to be tested at the nominal 5% level, without making adjustments for multiple comparisons.

### **9.2.3. Analysis of the Primary and Key Secondary Endpoints**

The primary analyses for both endpoints will be based on the FAS-RA subset. Secondary analyses will be based on the PPAS. For analysis of the primary and key secondary endpoints, a combination of graphical and analytical methods will be used. The time (in weeks) to protocol-defined flare will be used to evaluate the primary endpoint while the time (in weeks) to achieve an IGA score of  $\geq 2$  will be used to evaluate the key secondary endpoint. Subjects who do not report an event (ie protocol-defined flare or IGA  $\geq 2$ ) or discontinue the study during the double-blind randomized period will have their time to event censored at their last known visit in this period. Kaplan-Meier curves will be used to display the time to event and report the median time to event (and its 95% confidence interval) among the three randomized groups. The log-rank test will be used to compare these curves. Proportions of subjects with an event and confidence intervals will also be reported by randomized group.

### **9.2.4. Analysis of Secondary Endpoints**

In general, binary endpoints (such as EASI-50, EASI-90 or the proportion of subjects achieving  $\geq 4$  point improvement in severity of pruritus NRS measure) will be analyzed using the (Cochran-Mantel-Haenszel) test adjusted by randomization strata (age groups) and baseline disease severity. The difference between treatment groups in the proportion of subjects achieving a response along with its 95% confidence interval (using the normal approximation for the difference in binomial proportions) will be reported. If a subject withdraws from the study, then this subject will be counted as a non-responder for endpoints

after withdrawal. In addition, a subject in the FAS-RA subset who receives rescue treatment due to protocol-defined flare will be considered a non-responder.

For continuous endpoints, such as percent change from baseline in the EASI total score and BSA or change from baseline in SCORAD, PSAAD, DLQI/CDLQI, POEM, HADS, and change from baseline in the pruritus severity using the NRS measure, a mixed-effect model with repeated measures (MMRM) will be used. This model will include the factors (fixed effects) for treatment group, randomization strata (age groups), and baseline disease severity, visit, treatment-by-visit interaction, and relevant baseline value. Within the framework of MMRM, differences between groups will be tested using estimates from the MMRM model.

For all binary endpoints, missing data will be handled by considering subjects who withdraw or randomized subjects receiving rescue treatment as non-responders. No imputations will be made for continuous data and missing data will be considered to be MAR.

In general all secondary endpoints will be analysed for the FAS-RA subset. For the subjects requiring rescue therapy (FAS-RE subset), the response achieved at the end of the rescue period will be assessed in relation to the start of the rescue period. In addition to these two analysis sets, secondary endpoints will also be summarized for all subjects participating in the open-label run-in period (FAS-OL subset).

Hypotheses for all relevant secondary endpoints will be tested at the nominal 5% level of significance, without adjustments for multiple comparisons.

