3. ENDPOINTS AND BASELINE VARIABLES: DEFINITIONS AND CONVENTIONS

3.1. Primary Endpoint

Loss of response requiring rescue treatment will be evaluated in each group during the blinded treatment period. Loss of response is denoted as a flare and is defined as a loss of at least 50% of the Eczema Area and Severity Index (EASI) response at Week 12 and an Investigator's Global Assessment (IGA) score of 2 or higher.

Detailed descriptions of how the IGA and the EASI scores are derived are provided in [Appendix 3](#) and [Appendix 4](#) respectively.

Calculation for determining flare:

If x_0 is the EASI score at baseline and x_R is the EASI score at Week 12 (randomization), the EASI response at Week 12 (randomization) is defined as $x_R - x_0$. During the randomized, double-blind period, a subject would have met the definition of a flare if their EASI score is greater than or equal to $x_R + 0.5 \times |x_R - x_0|$ and their IGA score is greater than or equal to 2.

For example, if a subject has a total EASI score of 40 at baseline and a score of 10 at Week 12 (achieving EASI-75 to be a responder at randomization), the EASI response is -30. To meet the definition of flare, the total EASI score for this subject would have to go up by at least 15 (50% of -30) from Week 12, which computes to a total EASI score of at least 25, and in addition have an IGA score of ≥ 2 .

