3.4. Baseline Variables

Baseline values for demographics, medical history, primary diagnosis and prior drug treatments for atopic dermatitis will be based on measures collected at Visit 1/Screening visit or Day 1 visit. For analysis purposes, randomization strata information will be taken from the Case Report Form (CRF).

For all other analyses (including change from baseline), there are three possible choices for baseline in this study as,

Study Baseline: This baseline value will be defined as the last observation collected on or prior to Day 1 (first dose day) of study treatment. If a value is missing on Day 1, then the last available observation before Day 1 will be used. For the PSAAD score, baseline will be defined as a simple average of all values recorded between Day -6 and Day 1.

Randomization Baseline: This baseline value will be defined as the last observation collected between last dose of run-in treatment and Day 1 (first dose day) of randomized treatment. For the PSAAD score, randomization baseline will be defined as a simple average of all values recorded between last dose of run-in treatment and Day 1 of randomized treatment.

Rescue Baseline: This baseline value will be defined as the last observation collected between last dose of blinded treatment and Day 1 (first dose day) of rescue treatment. For the PSAAD score, rescue baseline will be defined as a simple average of all values recorded between last dose of blinded treatment and Day 1 of rescue treatment.

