5.2.1. Analyses for Binary Data

For analyses where treatment comparisons are relevant, binary data at each scheduled visit will be analyzed by two approaches: (1) the test of hypothesis (and the p-value) between two pairwise treatment groups will be conducted by the Cochran-Mantel-Haenszel (CMH) statistic adjusting for the effect of randomization strata and disease severity (moderate [IGA=3] or severe [IGA=4]) at Study Baseline; p-values will be calculated from the CMH statistic; and (2) the proportion of responders in each treatment group will be summarized along with pairwise differences and their 95% confidence intervals obtained by normal approximation. The difference in proportions will be calculated within each stratum. The final estimate of the difference in proportions will be a weighted average of these stratum-specific estimates using CMH weights. The CMH weight w_k for stratum k ($k = 1, 2, \dots, K$) is given by,

$$w_k = \frac{\frac{n_{ik} n_{ck}}{n_{ik} + n_{ck}}}{\sum_{j=1}^K \frac{n_{ij} n_{cj}}{n_{ij} + n_{cj}}}$$

where n refers to sample size, the subscript c refers to a comparator group and the subscript i refers to a test group. The difference is estimated as $\hat{d} = \sum_{k=1}^K w_k (\hat{p}_{ik} - \hat{p}_{ck})$, where \hat{p} refers to the estimated relative frequency (or proportion of responders).

Two-sided 95% confidence intervals for the difference (based on a normal approximation) are formed by:

$$\hat{d} \pm 1.96 \sqrt{\sum_{k=1}^K w_k^2 \left(\frac{\hat{p}_{ik}(1 - \hat{p}_{ik})}{n_{ik}} + \frac{\hat{p}_{ck}(1 - \hat{p}_{ck})}{n_{ck}} \right)}$$

In the above formula for the variance of \hat{d} (under the square-root sign), when the number of responders is zero ($x = 0$), then \hat{p} will be replaced by $0.5/(n + 1)$. This change will be made only for calculating the variance of \hat{d} and not anywhere else. Estimates of the

difference in proportions along with the two-sided 95% confidence interval will also be provided for the PF-04965842 200 mg QD group versus the PF-04965842 100 mg QD group. No hypotheses will be tested. In analyses of responders, 95% confidence intervals will be calculated for the estimated proportion of response. The confidence interval is based on the normal approximation (or the Clopper-Pearson exact method when there are no or 100% responders).

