5.2.2. Analyses for Longitudinal Continuous Data

Mixed-effect, repeated measures (MMRM) models will be used. Fixed effects for visit, treatment group, treatment-by-visit interaction (where treatment comparisons are relevant), disease severity at Study Baseline and randomization stratification factor will be included in the model. Visit will be modeled as a categorical covariate. Unstructured covariance matrix will be assumed for the model errors. Compound symmetry covariance matrix will be used if the model with unstructured covariance doesn't converge.

When modeling the change from baseline values, the variable for visit will start with the first post-baseline visit, and the actual baseline value will be included as a covariate. At each visit, estimates of least square mean (LSM) values and the pairwise LSM differences between the treatment groups will be derived from the model. The corresponding p-values and 95% confidence intervals will also be derived from the model.

For analyses where treatment comparisons are not relevant, the MMRM model will not have treatment as a factor and only estimates of the LSM values along with their 95% confidence intervals by visit will be reported.

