5.3.2. Continuous Endpoints

For longitudinal continuous endpoints based on the FAS-OL or FAS-RE analysis sets, assuming that the missing data mechanism is missing at random (MAR), the data will be analyzed based on the full likelihood using a linear mixed-effect model with repeated measures for these continuous variables (see [Section 5.2.2](#)). This model will yield unbiased estimates and valid inferences in the presence of a missing data mechanism that is MAR.

In the context of analyses based on the FAS-RA analysis set, subjects requiring to enter the rescue phase of the study are considered dropouts from randomized treatment along with discontinuation from study during double blind period due to any reason. This implies that outcome values after this intercurrent event will be considered missing data. The determination of a protocol-defined flare event (or dropout) is based on past and current values for the total EASI score and the IGA score prior to dropout and not influenced by future (unobserved) values of these assessments beyond dropout. So the mechanism for such a dropout, conditional on the past and current values for total EASI score and IGA score, may be considered MAR. Therefore, the data may be analyzed based on the full likelihood using a linear mixed-effect model with repeated measures for these continuous variables (see [Section 5.2.2](#)). This model will yield unbiased estimates and valid inferences in the presence of a missing data mechanism that is MAR.

In general, for non-PRO continuous endpoints measured longitudinally, missing values post-baseline will not be imputed explicitly. For the continuous PRO variables such as pruritus NRS, DLQI/CDLQI, POEM, PSAAD and HADS, rules (if any) suggested by the developers of these instruments will be followed in calculating the outcome value in the presence of missing data. If these rules are not enough for imputing a value, then the missing values will be handled in the same way as other non-PRO variables.

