6.3. Secondary Endpoints (Efficacy)

6.3.1. Response Based on (IGA, EASI-50, EASI-75, EASI-90, EASI-100, NRS4 for Severity of Pruritus, SCORAD50 and SCORAD75, IGA + EASI-75)

	All Randomized Subjects	Randomized Subjects Requiring Rescue Treatment	Pre- Randomization Subjects
Summary	Proportion of subjects achieving a response at Weeks 12, 16, 28, 40 and 52	Proportion of subjects achieving a response at Rescue Weeks 2, 4, 8 and 12	Proportion of subjects achieving a response at Weeks 2, 4, 8 and 12
Population	FAS-RA	FAS-RE	FAS-OL
Baseline	Study (see Section 3.4)	Rescue (see Section 3.4)	Study (see Section 3.4)
Statistical Method	CMH and normal approximation as in Section 5.2.1 .	Normal approximation as in Section 5.2.1 .	Normal approximation as in Section 5.2.1 .
Missing Data	Missing values after dropout are defined as “non-response” (see Section 5.3.1)	Missing values after dropout are defined as “non-response” (see Section 5.3.1)	Missing values after dropout are defined as “non-response” (see Section 5.3.1)

6.3.2. Change from Baseline in (Total EASI Score, SCORAD (VAS) Pruritus and Sleep Sub-Scales, PP-NRS for Severity and Percent BSA)

	All Randomized Subjects	Randomized Subjects Requiring Rescue Treatment
Summary	Change from baseline at Weeks 12, 16, 28, 40 and 52	Percent change/Change from baseline at Rescue Weeks 2, 4, 8 and 12
Population	FAS-RA	FAS-RE
Baseline	Study (for Week 12); Randomization (for visits after Week 12) (see Section 3.4)	Rescue (see Section 3.4)
Statistical Method	MMRM as in Section 5.2.2	MMRM as in Section 5.2.2
Missing Data	Use observed data (see Section 5.3.2)	

Change from Study Baseline at Week 12 and its 95% CI will be estimated for each randomized treatment group using an MMRM analysis using data from Weeks 2, 4, 8 and 12. For PP-NRS, data will be included from Days 2 – 15, Weeks 4, 8 and 12.

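### After Week 12 the MMRMs leave out the Day 1 value of the score, so a collected prognostic covariate goes unused, most clearly for EASI and BSA

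*Protocol*

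**What the plan says.** Protocol 9.2.4 lists the MMRM terms and ends with "visit, treatment-by-visit interaction, and relevant baseline value". It does not say which baseline is meant, so the point cannot be read from the protocol alone.

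The SAP fills this in:

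- SAP 5.2.2: "disease severity at Study Baseline and randomization stratification factor will be included in the model". For change scores, "the actual baseline value will be included as a covariate". No interaction of that covariate with visit is stated.
- SAP 5.2.1 defines the severity factor as "disease severity (moderate [IGA=3] or severe [IGA=4]) at Study Baseline".
- SAP 6.3.2 (EASI, SCORAD itch and sleep, itch NRS, BSA) and SAP 6.4.1 (HADS, POEM, PSAAD, DLQI/CDLQI) give the baseline for FAS-RA as "Study (for Week 12); Randomization (for visits after Week 12").
- SAP 3.4 defines the Randomization Baseline as the "last observation collected between last dose of run-in treatment and Day 1 (first dose day) of randomized treatment".

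So at Weeks 16, 28, 40 and 52 each model holds age stratum, Day 1 IGA severity in two levels, and the Week 12 value of the score. It does not hold the Day 1 value of that score, and no reason is given.

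**The concern.** This is a randomized withdrawal design. Everyone randomized has IGA 0 or 1 and at least a 75% fall in EASI, so Week 12 EASI varies little and may say little about how severe the disease becomes once response is lost. Day 1 EASI varies much more, is required for eligibility, and enters the flare rule: under SAP 3.1 "a subject would have met the definition of a flare if their EASI score is greater than or equal to" the Week 12 score plus half the Day 1 to Week 12 change.

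If the Day 1 value predicts later scores given what is already in the model, leaving it out keeps explainable variation in the residual. The Week 16 to 52 confidence intervals are then wider than they need to be.

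**Working it through.** **1. The plan's own flare example.** Let `x0` be Day 1 EASI and `xR` Week 12 EASI. For `xR` below `x0`, the threshold `xR + 0.5|xR - x0|` equals `(xR + x0)/2`. With the SAP 3.1 example, (10 + 40)/2 = 25, which agrees with the SAP.

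**2. How much of the threshold comes from Day 1.** EASI-75 means `xR` ≤ 0.25 `x0`. The threshold therefore lies between 0.5 `x0` and (1 + 0.25)/2 = 0.625 times `x0`. The share due to `x0` is `x0/(x0 + xR)`, which is at least 1/1.25 = 80%.

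**3. Compression.** Entry requires EASI of at least 16 (Protocol 4.1) and the scale ends at 72 (Protocol 7.7.3). Day 1 EASI can span 16 to 72. Week 12 EASI in a randomized subject is at most 0.25 × 72 = 18.

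**4. Two subjects the model may not separate.** Both have Week 12 EASI 2; Day 1 EASI is 20 in one and 60 in the other. Their EASI thresholds for flare are (2 + 20)/2 = 11 and (2 + 60)/2 = 31. The planned EASI model gives both the same baseline score. If they share Day 1 IGA category, age group and arm, their covariates are identical.

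**5. Size of the possible gain.** Adding one covariate multiplies the SE by sqrt(1 − r²), where r is its partial correlation with the outcome given the terms already in the model. The documents give neither r nor an SD, so r is assumed. Equivalent n is 200/(1 − r²).

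| Assumed r | CI narrower by | 200 per arm acts like |
|---|---|---|
| 0 | 0% | 200 |
| 0.1 | 0.5% | 202 |
| 0.2 | 2.0% | 208 |
| 0.3 | 4.6% | 220 |
| 0.4 | 8.3% | 238 |

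**6. Illustrative EASI simulations, with all inputs assumed and the severity factor already fitted.**

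- *Longitudinal:* 200 per arm, flare rule of SAP 3.1, relapse as a fraction of the Day 1 to Week 12 drop, 64–66% of placebo and 11–14% of 200 mg missing at Week 52, 150 trials in each of two scenarios. The model SE of the 200 mg minus placebo difference at Weeks 28/40/52 fell from 0.74/0.80/0.86 to 0.70/0.76/0.81, and from 0.73/0.80/0.83 to 0.70/0.76/0.80. That is about 4% (1 − 0.80/0.83) to 6% (1 − 0.81/0.86). Empirical SDs fell from 0.69/0.81/0.97 to 0.66/0.74/0.90, and from 0.79/0.86/1.01 to 0.75/0.81/0.98, which is about 3% to 9%. At Week 52 the model SE was below the empirical SD with and without the covariate, so the model-based figures there are less reliable.
- *Single post-randomization visit, ANCOVA:* 200 per arm, 400 runs per scenario, several relapse patterns, no cut-off at rescue. The SE fell by 3.3% (0.932 to 0.901, partial r 0.25) up to 11.9% (0.976 to 0.859, SEs rounded, partial r 0.47).
- In the second simulation the two-level severity factor already recovered between about a tenth, (0.682 − 0.674)/(0.682 − 0.608) = 0.11, and a half, (0.678 − 0.644)/(0.678 − 0.606) = 0.47, of the total gain.

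**7. Stated figures.** The only power figure, 94% with 200 per arm, concerns time to flare. No MMRM covariate enters it, so it does not change.

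**The case against.** The strongest case against is that this is only a modest efficiency preference. Much of that stands:

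- A reader might infer that the models adjust for the Week 12 value alone. They do not: age stratum and Day 1 IGA severity are fitted, and the latter is a partial stand-in for Day 1 EASI.
- A reader might extend the compression argument to every score. The responder criteria contain no itch or PRO score, and only EASI was simulated. BSA is plausible because affected area is a component of EASI. For NRS, DLQI, POEM, HADS and PSAAD the documents do not show that the Week 12 value is restricted.
- The simulated gain is partly built in, because relapse was generated from the Day 1 to Week 12 drop. No relapse model, SD or missingness rate comes from the documents.
- Relapse is only partly seen. After rescue, "outcome values after this intercurrent event will be considered missing data". This weakens the argument but does not remove it for EASI, because the EASI level at which rescue is triggered itself rises with `x0`.
- A Day 1 value is not always available. PSAAD is collected only in selected countries, and Protocol 7.8 admits subjects who cannot complete the handheld PROs. Adding the covariate could drop such subjects.

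What the objection does not supply is a reason to leave out Day 1 EASI or BSA. Both are recorded at entry, and both simulations show a gain with severity already in the model.

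**Conclusion.** The point holds as a low-cost improvement to secondary analyses, clearest for EASI and plausible for BSA. Its size cannot be known from the documents. It is zero if the partial correlation is zero, 0.5% to 8.3% of CI width for r from 0.1 to 0.4, and about 3% to 12% of the SE in EASI simulations under assumed relapse patterns.

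Two stronger readings are not supported. The first is bias. SAP 5.3.2 argues that data are missing at random given past and current EASI and IGA. Since `x0` is one of those past values and is not in the EASI model, a reader might conclude that the estimates are biased. That would require later EASI to depend on `x0` after allowing for the Week 12 value, severity and the on-treatment visits already modelled. Nothing in the documents establishes this, and no bias was quantified. Adding `x0` would bring the EASI model closer to the stated argument, but that is a side benefit. The second is damage to the main conclusions. The MMRM endpoints are tested at a nominal 5% outside the gatekeeping sequence, the primary and key secondary endpoints use log-rank tests, and randomization protects the comparison without this covariate.

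**What to change.** In SAP 5.2.2, for FAS-RA change-from-baseline MMRMs at visits after Week 12, add the Study Baseline value of the endpoint and its interaction with visit. Give the Randomization Baseline value the same interaction, and keep that value and the Day 1 IGA severity factor. Name the two baselines in Protocol 9.2.4 if it is next amended.

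Apply this to EASI and BSA. Treat it as optional for itch and the PROs and, if it is used there, state how subjects without a Day 1 value are kept in the analysis.

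Cost: a sentence or two of SAP text, settled before unblinding. With four visits, two baseline covariates with visit-specific slopes take 8 parameters instead of the present 1, so 7 more, of which 4 are for the Day 1 value. That is small beside about 600 randomized subjects. Day 1 scores are already scheduled, so no new data are needed.

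In the same edit, reconcile SAP Appendix 1, which lists Randomization as the baseline for the FAS-RA change scores at Week 12 too, with SAP 6.3.2, which uses the Study Baseline there.
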